6.2 Exclusion Criteria

1) Medical Conditions

- a) Women who are pregnant or breastfeeding.
- b) Not applicable per Global Protocol Amendment 01.

2) Gastrointestinal Exclusion Criteria

- a) Current colonic adenomas or dysplasia diagnosed at the endoscopy performed at the end of treatment visit of the parent study or past confirmed colonic dysplasia in the parent study that has not been eradicated.

A participant with adenomatous polyps may be eligible if the polyps have been completely removed (documented) and the participant is free of polyps at enrollment (Day 1).

A participant with mucosal dysplasia may be eligible if the dysplasia has been completely removed/resected/eradicated (as applicable, documented), and the participant is free of dysplasia at enrollment (Day 1). This should be discussed with the BMS Medical Monitor/designee prior to enrollment.

Participants must be current with surveillance for dysplasia and screening for colorectal cancer (based on local guidelines).

3) Immune and Infectious Disease Exclusion Criteria

- a) Known serious infection, defined as any infection requiring hospitalization or treatment with parenteral (intramuscular [IM] or IV) antimicrobial agents (eg, antibiotics, antiviral, antifungal, or antiparasitic agents) within [REDACTED] of the first dose of study treatment.

Antibiotics used to cover a procedure such as endoscopy would not exclude the participant. Prophylactic antibiotic use should be discussed with the BMS Medical Monitor/designee.

Additionally, in the case of prior SARS-CoV-2 infection, symptoms must have resolved and, based on investigator assessment in consultation with the BMS Medical Monitor/designee, there are no sequelae that would place the participant at a higher risk by receiving investigational treatment.

- b) Not applicable per Global Protocol Amendment 01.

4) Prior/Concomitant Therapy

Prohibited concomitant medications are further detailed in [Section 7.7.1](#). Participants must also comply with the protocol requirements for restricted concomitant medications in [Section 7.7.2](#) and permitted medications in [Section 7.7.3](#).

- a) Have received any of the following therapies since the first dose of study treatment in the parent study or before Day 1 in Study IM011077:
 - i) Treatment with an immunomodulatory or biologic agent for the treatment of IBD.
 - ii) Treatment with an investigational agent other than deucravacitinib.
 - iii) Treatment with D-penicillamine, leflunomide, thalidomide, S1P inhibitors (eg, ozanimod, fingolimod, and etrasimod), or JAK inhibitors (eg, tofacitinib, upadacitinib, and filgotinib).
- b) Are currently receiving or require initiation of any of the following therapies:
 - i) Treatment with corticosteroids at a dose that exceeds the prednisone equivalent of [REDACTED] for adrenal insufficiency.
 - ii) Treatment with immunomodulatory agents (eg, azathioprine, 6-mercaptopurine, or methotrexate).
- c) Treatment with a live vaccine or live attenuated vaccine within [REDACTED] prior to Visit 1 of this trial.
Not applicable per Global Protocol Amendment 01.
Not applicable per Global Protocol Amendment 01.
Not applicable per Global Protocol Amendment 01.
- d) Not applicable per Global Protocol Amendment 01.
- e) Prophylactic antibiotic use should be discussed with the BMS Medical Monitor/designee.

5) Physical and Laboratory Test Findings

- a) Evidence of active or latent tuberculosis (TB; see [Section 9.4.6](#))
Participants diagnosed with latent TB infection (LTBI) in the parent study are eligible to continue in this study if (1) there are no current signs or symptoms of active TB, (2) the participant has received adequate documented treatment for LTBI within 5 years of screening in the parent study.
- b) Evidence of active hepatitis B virus (HBV) infection as defined in [REDACTED]
[REDACTED]
- c) Not applicable per Global Protocol Amendment 01.
- d) Not applicable per Global Protocol Amendment 01.
- e) Clinically significant abnormalities in laboratory testing at the second to last visit in the parent study or most current result available prior to Day 1 including (but not limited to):
 - i) **Hematology:**
 - (1) Hemoglobin level [REDACTED] g/dL
 - (2) White blood cell (WBC) count [REDACTED] $\times 10^9/L$ ($< 3000/mm^3$)
 - (3) Lymphocyte count [REDACTED] $\times 10^9/L$ ($< 750/mm^3$)
 - (4) Neutrophil count [REDACTED] $\times 10^9/L$ ($< 1000/mm^3$)
 - (5) Platelet count [REDACTED] $\times 10^9/L$ ($< 100,000/mm^3$)

ii) Renal Function:

- (1) Serum creatinine $> 2 \times$ upper limit of normal (ULN) or renal impairment based on an estimated glomerular filtration rate < 45 mL/min/1.73 m² (calculated using the Modification of Diet in Renal Disease equation)

iii) Liver-related Blood Tests and Liver Function:

- (1) Serum alanine aminotransferase (ALT) $> 2 \times$ ULN
- (2) Serum aspartate aminotransferase (AST) $> 2 \times$ ULN
- (3) Serum total bilirubin $> 1.5 \times$ ULN

Participants with total bilirubin $> 1.5 \times$ ULN who have a confirmed diagnosis of Gilbert's syndrome are not excluded from this study but must be discussed with the BMS Medical Monitor/designee.

- (4) Alkaline phosphatase (ALP) $> 1.5 \times$ ULN

- f) Any other findings on physical examination, vital signs, or clinical laboratory testing that, in the opinion of the investigator, may place the participant at an unacceptable risk for participation in this study.

6) Allergies and Adverse Drug Reaction

- a) History of any significant drug allergy (eg, anaphylaxis) or significant adverse drug reaction (eg, hepatotoxicity).

7) Other Exclusion Criteria

- a) Participants with cancer screening or surveillance that is suspicious for malignancy, or where the possibility of malignancy cannot be reasonably excluded after additional clinical, laboratory, or other diagnostic evaluations. Participants with non-melanoma skin cancer are not excluded.
- b) Class III or IV congestive heart failure, as classified by the New York Heart Association (NYHA) Functional Classification or any recent onset of heart failure resulting in NYHA Class III/IV symptoms.
- c) Acute coronary syndrome (eg, myocardial infarction, unstable angina pectoris) and/or any history of significant cerebrovascular disease (eg, stroke, cerebral hemorrhage, transient ischemic attack) within 24 weeks before enrollment.
- d) Known history of hereditary galactose intolerance, total lactase deficiency, or glucose-galactose malabsorption.
- e) Prisoners or participants who are involuntarily incarcerated. (Note: Under certain specific circumstances and only in countries where local regulations permit, a person who has been imprisoned may be included or permitted to continue as a participant. Strict conditions apply, and Bristol-Myers Squibb approval is required.

Eligibility criteria for this study have been carefully considered to ensure the safety of the study participants and that the results of the study can be used. It is imperative that participants fully meet all eligibility criteria.

6.2.1 Enrollment Criteria

Participants must meet the following criteria at the enrollment visit on Day 1 in order to be eligible to be enrolled into Study IM011077 and to receive the first dose of deucravacitinib on this study:

- 1) The participant continues to meet the **inclusion criteria**, listed in [Section 6.1](#).
- 2) The participant continues to not meet any of the **exclusion criteria**, listed in [Section 6.2](#).
- 3) The participant has discontinued any **prohibited treatments** ([Section 7.7.1](#)).

6.3 Lifestyle Restrictions

Participants are required to fast for a minimum of [REDACTED] before the enrollment visit (Day 1), [REDACTED] because fasting lipid panel and glucose samples will be obtained at these visits.

6.3.1 Meals and Dietary Restrictions

Study treatment may be taken without regard to meals.

6.3.2 Tobacco and e-Cigarettes

Smoking can have an influence on the severity of IBD disease symptoms. Consequently, use of tobacco products will be assessed at each study visit. Use of a nicotine patch or other nicotine supplements should be recorded as concomitant medication.

6.3.3 Activity

No activity restrictions are required.

6.4 Enrollment Failures

Enrollment failures are defined as participants who consent to participate in the clinical study but who are not subsequently entered in the study/included in the analysis population. A minimal set of enrollment failure information is required to ensure transparent reporting of enrollment failure participants, to meet the Consolidated Standards of Reporting Trials (CONSORT) publishing requirements, as applicable, and to respond to queries from regulatory authorities. Minimal information includes date of consent, demography, enrollment failure details, eligibility criteria, and any SAEs.

7 TREATMENT

Study treatment is defined as any investigational treatment(s), marketed product(s), placebo, or medical device intended to be administered to a study participant according to the study randomization or treatment allocation.

Study treatment includes both Investigational [Medicinal] Product (IP/IMP) and Non-investigational [Medicinal] Product (Non-IP/Non-IMP) and can consist of the following:

- IP
 - Deucravacitinib

An IP, also known as IMP in some regions, is defined a pharmaceutical form of an active substance or placebo being tested or used as a reference in a clinical study, including products already with a marketing authorization but used or assembled (formulated or packaged) differently than the authorized form, or used for an unauthorized indication, or when used to gain further information about the authorized form.

Other medications used as support or escape medication for preventative, diagnostic, or therapeutic reasons, as components of the SOC for a given diagnosis, may be considered as Non-IP.

Table 7-1: Study Treatments for Study IM011077

Product Description/ Class and Dosage Form	Potency	IP/Non-IP	Blinded or Open Label	Packaging/ Appearance	Storage Conditions (per label)
Deucravacitinib (BMS-986165) oral tablet	6 mg	IP	Open label	Bottles containing  tablets	Store at 15°-25°C in a tightly closed container and protected from light

Abbreviation: IP = Investigational Product.

7.1 Treatments Administered

Participants will take deucravacitinib 6 mg BID by taking 1 tablet in the morning and 1 tablet in the evening. Study treatment will be supplied in bottles containing  tablets. Bottles are to be stored at 15°C to 25°C in a tightly closed container and protected from light.

The selection and timing of dose for each participant is as follows:

Table 7.1-1: Selection and Timing of Dose

Study Treatment	Unit Dose Strength(s)/Dosage level(s)	Dosage Formulation Frequency of Administration	Route of Administration
6 mg BID Deucravacitinib (BMS-986165)	6 mg	1 active tablet in the morning; 1 active tablet in the evening	Oral

Abbreviation: BID = twice daily.

Deucravacitinib can be administered with or without food, and there are no precautions or restrictions to the administration of antacids with deucravacitinib.

7.2 Method of Treatment Assignment

All participants will be assigned to treatment using an Interactive Response Technology (IRT). Before the study is initiated, each user will receive login information and directions on how to access the IRT.

At the time of the first visit in Study IM011077, immediately after informed consent is obtained and before any study-related procedures are performed, the investigative site will access the enrollment option of the IRT system for assignment of a participant number for all participants into the open-dose panel. Enrolled participants, including those not dosed, will be assigned sequential participant numbers starting with [REDACTED]. The participant identification number (PID) will be comprised of a 4-digit site number and 5-digit participant number. For example, the first participant enrolled at site number 1 will have a PID of [REDACTED]. The participant number will not be used for any other participant. For continuity purposes, the participant number from the parent study will be recorded for each participant enrolled in IM011077.

Study treatment will be dispensed at the study visits as listed in Schedule of Activities ([Section 2](#)).

7.3 Blinding

This is a nonrandomized, open-label study; blinding procedures are not applicable.

7.4 Dosage Modification

There is no provision for dose modification of study treatment. Dose modification of study treatment may be allowed for safety reasons or if recommended by the independent DMC. Such cases will be discussed with the BMS Medical Monitor/designee prior to any study treatment modification.

Modification of permitted CD or UC treatments or dose regimens is allowed for safety reasons, or if a participant experiences an AE attributable to that treatment. Participants should continue to take their assigned treatment even if their clinical condition worsens (ie, they experience disease exacerbation or a “flare”), unless any of the criteria in [Section 8.1](#) (Discontinuation Criteria) are met. If a participant’s clinical condition worsens to the extent that rescue therapy (other than permitted therapy) is required, based on the investigator’s judgment, the participant must discontinue study treatment in favor of appropriate alternative available treatment.

If treatment is interrupted for a participant due to an AE, study treatment can be restarted in consultation with the BMS Medical Monitor/designee if the AE is not serious and assessed as not related to study treatment.

7.5 Preparation/Handling/Storage/Accountability

The IP should be stored in a secure area according to local regulations. It is the responsibility of the investigator to ensure that IP is only dispensed to study participants. The IP must be dispensed only from official study sites by authorized personnel according to local regulations.

The product storage manager should ensure that the study treatment is stored in accordance with the environmental conditions (temperature, light, and humidity) as determined by BMS. If concerns regarding the quality or appearance of the study treatment arise, the study treatment should not be dispensed, and contact BMS immediately.

IP documentation (whether supplied by BMS or not) must be maintained that includes all processes required to ensure drug is accurately administered. This includes documentation of drug storage, administration, and storage temperatures.

Please refer to the current version of the IB for complete storage and handling information.

Further guidance and information for final disposition of unused study treatment are provided in [Appendix 2](#) and the Study Reference Manual.

7.5.1 **Retained Samples for Bioavailability/Bioequivalence/Biocomparability**

Not applicable.

7.6 **Treatment Compliance**

Study treatment compliance will be monitored as indicated in [Section 2](#) (Schedule of Activities) using standard drug accountability procedures (comparing the number of [REDACTED] returned to number dispensed, considering the expected regimen and any reported missed doses). Drug accountability will be reviewed by the investigative site staff at each visit to confirm treatment compliance. Site staff will discuss any discrepancies with the participant and remind the participant of the importance of compliance with the assigned regimen.

7.7 **Concomitant Therapy**

All medications taken from within [REDACTED] before the first dose of study treatment until [REDACTED] after the last dose of study treatment or last visit (whichever comes later) must be recorded on the appropriate eCRF.

Other than existing treatment for CD or UC (with restrictions as described in the eligibility criteria ([Section 6](#) [Study Population])), concomitant medications (prescription, over-the-counter [OTC], or herbal) should be administered during the study only if they are prescribed for treatment of specific medical reasons separate from CD or UC.

7.7.1 **Prohibited Treatments**

Prohibited prior and current concomitant medications are summarized in Table 7.7.1-1. Medications taken within [REDACTED] prior to study treatment administration must be recorded on the eCRF.

Table 7.7.1-1: Summary of Prohibited Concomitant Medications

Prohibited Treatments	
Medication/Formulation	Notes
Corticosteroids: Prednisone [REDACTED] or budesonide MMX [REDACTED], for the treatment of CD or UC.	[REDACTED]
Corticosteroids: A course of IV or IM corticosteroids (> 24 hours in duration) or more than 1 discrete exposure to IV or IM	IV or IM corticosteroids are prohibited prior to Day 1 and during the study treatment period.

Table 7.7.1-1: Summary of Prohibited Concomitant Medications

Prohibited Treatments	
Medication/Formulation	Notes
corticosteroids (< 24 hours in duration) required to treat CD or UC.	
Immunomodulatory drugs	Prohibited during study
Biologic drugs for IBD	Prohibited during study
Live vaccines	Prohibited from the parent study EOT visit, during the study, or within the [REDACTED] after the last dose. ^a
Apheresis	Prohibited from parent study EOT visit and during the study.
Investigational agents (other than deucravacitinib)	Prohibited from the parent study EOT visit and during the study.
Traditional Chinese medicines, herbal medicines, or herbal supplements	Prohibited from the parent study EOT visit and during the study; only exceptions are: medicines/supplements that were previously approved by the BMS Medical Monitor/designee in the parent study or a new exception that has been cleared by the BMS Medical Monitor/designee.

Abbreviations: BMS = Bristol-Myers Squibb; CD = Crohn’s disease; EOT = end of treatment; IBD = inflammatory bowel disease; IM = intramuscular; IV = intravenous; mg = milligram; MMX = Multi-Matrix System; [REDACTED] UC = ulcerative colitis.

^a Heat-killed (or otherwise inactivated) or protein or subunit vaccines such as influenza and pneumococcal vaccines may be received at any time during the study. [REDACTED]

7.7.2 Restricted Concomitant Medications

Restricted concomitant medications are summarized in Table 7.7.2-1. Restricted medications taken within [REDACTED] prior to study treatment administration must be recorded on the eCRF.

Table 7.7.2-1: Summary of Restricted Concomitant Medications

Restricted Treatments	
Medication/Formulation	Notes
Corticosteroid Rescue Therapy (Section 7.7.4) Systemic corticosteroids required to treat CD or UC	[REDACTED]

Table 7.7.2-1: Summary of Restricted Concomitant Medications

Restricted Treatments	
Medication/Formulation	Notes
Corticosteroids: Topical, inhaled, intra-articular or intrabursal, to treat non-IBD medical conditions	Allowed but must be discussed with the BMS Medical Monitor/designee.
Corticosteroids: Systemic corticosteroids ██████████ to treat non-IBD medical conditions	Allowed but must be discussed with the BMS Medical Monitor/designee to determine if the intercurrent illness affects the safety of the participant or if the corticosteroid treatment is likely to confound efficacy assessment.
Nonsteroidal anti-inflammatory drugs	May be used on an as needed basis during the study, but use is not recommended, as NSAIDs may be associated with GI toxicity, including mucosal injury.

Abbreviations: BMS = Bristol-Myers Squibb; CD = Crohn’s disease; GI = gastrointestinal; IBD = inflammatory bowel disease; NSAID = nonsteroidal anti-inflammatory drug; UC = ulcerative colitis.

7.7.3 Permitted Medications

Use of concomitant rectally administered corticosteroids and 5-aminosalicylic acid (5-ASA) are permitted throughout the study.

Use of concomitant oral 5-ASA is permitted per the country label or institutional practice. Dose modification of 5-ASA is allowed during the study if this is required to optimize therapy and for participant safety reasons, such as if a participant experiences an AE attributable to 5-ASA. The rationale for dose modification must be documented in source documents. The AE or SAE eCRF must be completed, if applicable.

Oral corticosteroids for adrenal insufficiency are allowed at a maximum dose of prednisone ██████████ or equivalent. Probiotics are allowed with no restrictions on use. Participants will continue their existing IBD treatment(s) during the study, provided the treatment complies with the eligibility criteria (see [Sections 6.1](#) [Inclusion Criteria] and [6.2](#) [Exclusion Criteria] and [Table 7.7.1-1](#) and [Table 7.7.2-1](#)).

7.7.4 Disease Exacerbation, Corticosteroid Rescue Therapy, and Tapering

7.7.4.1 Disease Exacerbation

Participants who are experiencing symptoms of possible disease exacerbation (loss of response for CD or disease worsening for UC as defined in [Table 4-1](#) and [Table 4-2](#)) should be evaluated as deemed appropriate by the investigator in order to determine whether corticosteroid rescue therapy may be appropriate. Participants who are seen by the investigator due to disease exacerbation should undergo the following assessments:

- Symptom-directed physical examination including vital signs
- Assessment of disease activity

- [REDACTED] complete blood count, and additional laboratory assessments, as indicated
- Stool sample for culture, ova, and parasite evaluation, and *Clostridioides. difficile* assay
- [REDACTED]
- Endoscopy may be considered and performed

Upon confirmation of loss of response or disease worsening, corticosteroid rescue therapy or alternative efficacious therapy for IBD may be initiated. If the participant still meets the criteria for loss of response or disease worsening [REDACTED] after first presenting with symptoms and despite treatment, he/she should be identified as a treatment failure, be discontinued from study treatment (Sections 5.1.4 and 8.1), and enter the post-treatment follow-up period (Section 5.1.3).

If an alternative, efficacious therapy for IBD is determined to be the appropriate course of action, the participant will be identified as a treatment failure and must be discontinued from study treatment (Sections 5.1.4 and 8.1).

Corticosteroid rescue therapy and the subsequent tapering is described in detail in Section 7.7.4.2.

7.7.4.2 Corticosteroid Rescue Therapy and Tapering

[REDACTED]

[REDACTED] Failure to taper the corticosteroid dose to 0 mg daily [REDACTED] of initiation will be considered treatment failure, and participants must discontinue from the study, unless the participants require glucocorticoid treatment for adrenal insufficiency. Participants who remain on corticosteroids to treat adrenal insufficiency must be discussed with the BMS Medical Monitor/designee to continue the study. Rescue therapy with medications other than oral corticosteroids, including immunosuppressants or biologics for IBD, are not permitted.

Oral corticosteroid rescue therapy [REDACTED] may be used [REDACTED] in response to an increase in CD or UC disease activity at the investigator's discretion (refer to [REDACTED]). The oral corticosteroid should be tapered upon demonstrated disease improvement per investigator judgement. The recommended corticosteroid taper is as follows:

- [REDACTED]
- [REDACTED]
- [REDACTED]
- [REDACTED]

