5.1.2 Treatment Period

At the Day 1 study visit, participants who have met the eligibility criteria for this study will be assigned a unique study identification number ([Section 7.2](#) [Method of Treatment Assignment]) and study treatment will be dispensed. On Day 1, after the informed consent is obtained, study treatment should be taken at the site from Study IM011077.

Prior to each scheduled visit, the participant [REDACTED] should be reviewed to ensure [REDACTED] stool frequency (SF) and RB data [REDACTED] for participants with UC. Prior to each scheduled visit at which Mayo scores are to be calculated, study personnel should ascertain whether an adequate number of days [REDACTED] have been made. If adequate [REDACTED] have not been made, the site should contact the participant to reschedule the visit (within the allowed [REDACTED]) to allow time for a sufficient number [REDACTED] for endpoint assessments, and the participant should be counseled about proper study procedures.

[REDACTED] It is recommended that the endoscopy be done as close as possible to the relevant visit.

If a colonoscopy is performed at the end of treatment visit of the parent study, colonoscopy will be the preferred endoscopic procedure for subsequent endoscopies within the study. This approach will facilitate comparison between the individual colonic segments assessed at the Day 1 visit and subsequent assessments.

Discontinuation criteria are detailed in [Section 8](#). Participants who temporarily discontinue study treatment will remain in the study and continue to participate in study procedures ([Section 8.1.1](#)).

Participants who permanently discontinue study treatment will complete an early termination (ET) visit and must enter the 4-week post-treatment follow-up period and complete the final safety visit.

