5.1.3 Follow-up Period

Participants who complete the treatment period (ie, Week 288) or permanently discontinue study treatment at any time during the study (Section 8) will enter a 4-week post-treatment follow-up period and complete the final safety visit.

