8 DISCONTINUATION CRITERIA

8.1 Discontinuation From Study Treatment

Participants MUST discontinue study treatment (and non-study treatment at the discretion of the investigator) for any of the following reasons:

- Participant's request to stop study treatment. Participants who request to discontinue study treatment will remain in the study and must continue to be followed for protocol-specified follow-up procedures. The only exception to this is when a participant specifically withdraws consent for any further contact with him/her or persons previously authorized by participant to provide this information.
- Participant meets any of the criteria for treatment failure defined in [Section 5.1.4](#) (Treatment Failure), [REDACTED].
- Any clinical AE, laboratory abnormality, or intercurrent illness which, in the opinion of the investigator, indicates that continued participation in the study is not in the best interest of the participant.
- Participant who develops a significant infection during the study defined as any infection (viral, bacterial, and fungal) considered by the investigator to be related to IP [REDACTED]
- Any drug-related rash or hypersensitivity reaction (eg, anaphylaxis, angioedema, urticaria, Stevens-Johnson syndrome, [REDACTED])
- Pregnancy, [REDACTED]
- Participant meets any of the following criteria for liver-related laboratory abnormalities. If these abnormalities are identified, repeat testing should occur within 48 to 72 hours and these results should be discussed with the BMS Medical Monitor/designee. Additional

recommendations on the recognition and investigation of potential drug-induced liver injury (DILI) are given in [Section 9.2.7](#) (Potential Drug-induced Liver Injury).

- ALT or AST $> 8 \times$ ULN on a single occasion
- ALT or AST $> 5 \times$ ULN for more than 2 weeks
- ALT or AST $> 3 \times$ ULN and total bilirubin $> 2 \times$ ULN or international normalized ratio (INR) > 1.5
- ALT or AST $> 3 \times$ ULN with the appearance of fatigue, nausea, vomiting, right upper quadrant pain or tenderness, fever, rash, and/or eosinophilia ($> 5\%$)
- Participant meets 1 of the following criteria for laboratory abnormalities in 2 sequential laboratory measurements taken 3 to 5 days apart:
 - Hemoglobin < 7.0 g/dL 
 - WBC count $< 1.5 \times 10^9/L$ ($< 1,500/mm^3$)
 - Absolute lymphocyte count $< 0.5 \times 10^9/L$ ($< 500/mm^3$)
 - Absolute neutrophil count $< 0.75 \times 10^9/L$ ($< 750/mm^3$)

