 - Platelet count $< 75 \times 10^9/L$ ($< 75,000/mm^3$)
 - An increase in serum creatinine $> 50\%$ over the IM011077 study baseline (Day 1) values and an absolute increase in serum creatinine > 0.5 mg/dL ($> 44.2 \mu\text{mol/L}$)
 - Creatine kinase elevations $> 10 \times$ ULN, unless the causality is known not to be medically serious (eg, exercise induced)
- Inability or failure to comply with protocol requirements.
- Termination of the study by BMS
- Loss of ability to freely provide consent through imprisonment or involuntarily incarceration for treatment of either a psychiatric or physical (eg, infectious disease) illness. (Note: Under specific circumstances and only in countries where local regulations permit, a participant who has been imprisoned may be permitted to continue as a participant. Strict conditions apply and BMS approval is required.)

Refer to [Section 2](#) (Schedule of Activities) for data to be collected at the time of treatment discontinuation and follow-up and for any further evaluations that can be completed.

All participants who discontinue study treatment should comply with protocol specified follow-up procedures as outlined in [Section 2](#) (Schedule of Activities). The only exception to this requirement is when a participant withdraws consent for all study procedures, including post-treatment study

follow-up, or loses the ability to consent freely (ie, is imprisoned or involuntarily incarcerated for the treatment of either a psychiatric or physical illness).

If study treatment is discontinued prior to the participant's completion of the study, the reason for the discontinuation must be documented in the participant's medical records and entered on the appropriate eCRF page.

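### Section 7.7.4.2 takes corticosteroid-taper failures out of the study, while the other sections stop study treatment and keep follow-up; read literally, 28-day safety data could be missed

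*Combined protocol and SAP*

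**What the plan says.** Section 7.7.4.2 covers corticosteroid rescue and tapering. A participant who cannot be tapered to zero within the time limit (redacted) "will be considered treatment failure, and participants must discontinue from the study, unless the participants require glucocorticoid treatment for adrenal insufficiency". Those kept on steroids for adrenal insufficiency must be discussed with the Medical Monitor if they are to continue in the study, so this section speaks of study participation throughout.

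The neighbouring and general sections speak of study treatment:

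- Section 7.7.4.1, loss of response or disease worsening that persists despite treatment: "he/she should be identified as a treatment failure, be discontinued from study treatment", and the same sentence sends the participant into post-treatment follow-up.
- Section 7.7.4.1, alternative therapy chosen: "the participant will be identified as a treatment failure and must be discontinued from study treatment".
- Section 8.1 lists as a reason to stop study treatment: "Participant meets any of the criteria for treatment failure defined in" Section 5.1.4. It adds: "All participants who discontinue study treatment should comply with protocol specified follow-up procedures as outlined in" the Schedule of Activities. The exceptions are withdrawal of consent for all procedures and loss of the ability to consent freely.
- Section 5.1.2: "Participants who permanently discontinue study treatment will complete an early termination (ET) visit and must enter the 4-week post-treatment follow-up period", and they complete the final safety visit.
- Section 5.1.3: those who finish treatment or stop permanently "will enter a 4-week post-treatment follow-up period and complete the final safety visit".

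Sections 5.1 and 8.1.2 agree with this second group. Section 8.2, headed as discontinuation from the study, does not mention treatment failure.

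**The concern.** The protocol gives stopping treatment (8.1) and leaving the study (8.2) separate sections, so the choice of words has operational meaning. One label, treatment failure, here carries two dispositions. Section 7.7.4.1 refers the reader to 7.7.4.2 for the detail of rescue and tapering, and the visible text of 7.7.4.2 does not point back to 8.1, 5.1.2 or 5.1.3.

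Safety is the primary objective, and Section 9.2.1 collects adverse events up to the Final Safety Visit. A site coordinator who works from 7.7.4.2 alone could close out a taper failure without the ET visit or the Final Safety Visit. The participants concerned have active disease and recent systemic steroids on top of a drug that Section 3.3 calls a potential immunosuppressant, and Section 9.2.8 lists infections among the potential events of interest. Any gap would therefore not fall at random.

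The same ambiguity touches counting. The primary endpoint in Section 10.3.1 refers to adverse events leading to study discontinuation, while Section 10.4.2.1 plans a summary of those leading to discontinuation of study treatment. If disposition is unclear, so is the category in which some of these participants belong.

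**Working it through.** The plan has no figure to reproduce: Section 10.1 makes no sample-size or power calculation, and no rate of taper failure is given. The check is a comparison of text, followed by a bound on what could be missed.

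**Text.** What each section does with the participant:

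| Section | Trigger | Leaves | Follow-up named |
|---|---|---|---|
| 7.7.4.2 | failed taper | the study | none in visible text |
| 7.7.4.1 | persisting loss of response or worsening | study treatment | post-treatment follow-up |
| 7.7.4.1 | alternative therapy | study treatment | none in that sentence |
| 8.1 | treatment failure per 5.1.4 | study treatment | Schedule of Activities procedures |
| 5.1.2 | any permanent stop | study treatment | ET visit, 4 weeks, final safety visit |
| 5.1.3 | completion or any permanent stop | study treatment | 4 weeks, final safety visit |
| 5.1, 8.1.2 | any stop of study treatment (5.1: permanent, before Week 288) | study treatment | Final Safety Visit (5.1); 28 days or longer (8.1.2) |

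Only 7.7.4.2 removes the participant from the study. Of the four sections it must be reconciled with, only 5.1.2 names the ET visit in its text.

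**Bound.** Inputs: N = 300 (Section 10.1); window = 28 days (Section 8.1.2); proportion p failing the taper, assumed. The formula is person-years = N × p × 28 / 365.25.

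- p = 3%: 300 × 0.03 = 9 participants; 9 × 28 / 365.25 = 0.69 person-years.
- p = 10%: 300 × 0.10 = 30 participants; 30 × 28 / 365.25 = 2.30 person-years.
- Wider range, p = 1% to 30%: 3 to 90 participants, 0.23 to 6.90 person-years.

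For scale, full treatment exposure with no dropout is 300 × 288 × 7 / 365.25 = 1,656 person-years. The 3 to 10% range is then 0.69 / 1,656 = 0.04% to 2.30 / 1,656 = 0.14%. Attrition would raise these shares, but no dropout rate is given.

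Expected serious events missed = person-years × rate. At p = 10% and an assumed 5 to 40 serious events per 100 person-years: 2.30 × 0.05 = 0.12 to 2.30 × 0.40 = 0.92.

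All of these are upper bounds, because they suppose that every site skips follow-up for every taper failure. They cover the 28-day window only; the ET assessments would be missed in addition.

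**The case against.** The strongest reply is that follow-up of taper failures is already required elsewhere. Section 7.7.4.2 waives no visit and does not say that removal is immediate. Leaving the study also ends study treatment for good, so 5.1.2, 5.1.3, 8.1, 8.1.2 and 9.2.1 apply on their own terms. The protocol also uses the language of study discontinuation for people who are still followed: Section 9.2.5 stops study treatment for pregnancy and then calls for study-discontinuation and follow-up procedures. The amendment's stated reason for the current 5.1.2 and 5.1.3 text was to make sure that those who leave the study complete the safety visit.

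This stands as far as it goes. It rules out the stronger reading that a reader might take from 7.7.4.2, namely that the protocol discards these data by design. It does not remove the conflict, since the harmonious reading has to be assembled from several sections that 7.7.4.2 does not cite.

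Redaction is a fair caution. The text before the sentence, the time limit, much of the first criterion in 5.1.4 and a qualifier on the 8.1 entry are blacked out. Whether 5.1.4 itself lists taper failure cannot be seen. But 7.7.4.2 applies the treatment-failure label in its own visible words, and the clause ordering exit from the study is legible.

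**Conclusion.** The contradiction is real and lies in operative text. Its consequence is conditional: if 7.7.4.2 is followed literally, ET assessments and adverse event and laboratory data from the 28 days after the last dose could be missed for taper failures. The amount is unknown. The 0.7 to 2.3 person-years rest on an assumed 3 to 10% failure rate and on universal non-follow-up, and are small beside the planned exposure. What justifies the correction is the primary safety objective and the kind of participant affected, more than the volume of data.

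Three further inferences are not supported. A reader might conclude that the loss would favour the drug, but the documents give no event rate for this group and the study is uncontrolled. A reader might take 8.2 to make withdrawal of consent the sole exception to follow-up for everyone. That sentence concerns participants who ask to stop treatment, and the general rule in 8.1 has two exceptions. A reader might also count a routine ECG at the Final Safety Visit as lost, but the schedules require it only if the ET tracing was abnormal.

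**What to change.** Reconcile 7.7.4.2 with 7.7.4.1, 8.1, 5.1.2 and 5.1.3 so that discontinuation of the study and of study treatment are used consistently. State in 7.7.4.2 that the existing ET visit, Final Safety Visit and adverse event collection apply to participants who fail the taper, as they do to other permanent treatment discontinuations. Use the same term in the Section 10.3.1 endpoint and the Section 10.4.2.1 summary.

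The cost is about one clause in 7.7.4.2 and a matching term in Section 10. No visit or procedure is added. The clinical rule on when a participant must stop is left to the sponsor.
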